## LIST OF ABBREVIATIONS

ACCORD	Academic and Clinical Central Office for Research & Development - Joint office for The University of Edinburgh and Lothian Health Board
CI	Chief Investigator
CRF	Case Report Form
ECS	Environmental Control Service
GCP	Good Clinical Practice
ICH	International Conference on Harmonisation
PI	Principal Investigator
QA	Quality Assurance
REC	Research Ethics Committee
SOP	Standard Operating Procedure

# **1 INTRODUCTION**

## **1.1 BACKGROUND**

Within the UK there are over 15 million people who live with at least one long term condition. Of these people, over 4 million suffer from mental health problems (Naylor C. 2012). A study by Emerson et al (2009) found that people with disabilities have poorer mental health than their counterparts.

Environmental control systems are a type of assistive technology that can be controlled by a wide variety of different access methods (e.g. switches) and can assist people with physical disabilities to control various electronic devices in the home environment. The systems are designed to provide independence, removing the requirement to be reliant on other people (for the operation of the controlled devices) and potentially could have a positive effect on mental health and quality of life.

A systematic review carried out by Brandt et al. (2010) concluded that there was not enough evidence to conclusively say that environmental control systems improve outcomes for patients. Whilst the review did not specifically investigate mental health outcomes it did look at quality of life and user satisfaction. There is a paucity of studies specifically focusing on mental health outcomes. A study by Squires et al. (2021) did include some mental health outcome measures. However, it was a case study with one participant and it is therefore not possible to draw any conclusions for a wider population. This project aims to address the issues above by determining the impact of environmental control systems on mental health by recording outcome measures pre and post intervention.

## **1.2 RATIONALE FOR STUDY**

The research question for this study is to determine impact of environmental controls on mental health. It is hypothesised that there will be a positive impact on mental health of the participants.

This study will contribute to an evidence base for the importance and value of environmental control systems. This evidence base can be used as part of a review of the NHS Scotland service provision of environmental controls and writing and implementing a national service specification for environmental controls in Scotland.

# **2 STUDY OBJECTIVES**

## **2.1 OBJECTIVES**

### **2.1.1 Primary Objective**

To explore the impact of environmental controls on the user's mental health and quality of life.

## **2.2 ENDPOINTS**

[figure not shown]
### **2.2.1 Primary Endpoint**

The co-primary endpoints are the PROMIS Global10 and PIADS-10 measures.

NB due to predicted low participant numbers this study has not been powered to assess these endpoints. Instead the data will be analysed with descriptive methods with a focus on clinical significance.

### 3 STUDY DESIGN

Case series (follow-up) design. Participants will be involved from their assessment until 8 weeks after device provision. The full duration of involvement will vary depending on assessment wait times and availability of required intervention. The study will take place in the participant's home.

### 4 STUDY POPULATION

#### 4.1 NUMBER OF PARTICIPANTS

The participants will be recruited from the population served by NHS Lothian's Environmental Control Service. The number of participants will be determined by how many participants it is possible to recruit within 12 months – it is expected to be <10. The participants will be referred to service as normal and the clinical intervention (supply of an environmental control system) will proceed irrespective of their participation or otherwise in the study. The only difference to the normal service provision and pathway is the application of the baseline and follow up questionnaires.

## **4.2 INCLUSION CRITERIA**

- i. Eligible for an environmental control system (age 18-80).
- ii. New user (no previous intervention).
- iii. Neurological condition.
- iv. Cognitive ability to answer the questions and to give consent.

## **4.3 EXCLUSION CRITERIA**

- i. Previous environmental control intervention
- ii. Patients requiring equipment not supplied by NHS Lothian's ECS (e.g. door interface)
- iii. Patient recently diagnosed (within 6 months)
- iv. Rapidly deteriorating condition

## **4.4 CO-ENROLMENT**

Co-enrolment will not be allowed in any circumstances.

# **5 PARTICIPANT SELECTION AND ENROLMENT**

## **5.1 IDENTIFYING PARTICIPANTS**

Participants will be identified by Clinical Scientists working in NHS Lothian's Environmental Control Service (ECS). The patient will be contacted by a Clinical Scientist via telephone, to arrange an environmental control assessment, at which point they will be approached to join the study.

## **5.2 CONSENTING PARTICIPANTS**

Informed consent will be collected by a Clinical Scientist at the assessment appointment in the form of a consent form. The participants will be sent the information sheet at least 1 week in advance of the assessment appointment.

### **5.2.1 Withdrawal of Study Participants**

Participants are free to withdraw from the study at any point or a participant can be withdrawn by the Investigator. If withdrawal occurs, the primary reason for withdrawal will be documented in the participant's case report form, if possible. The participant will have the option of withdrawal from:

- (i) all aspects of the trial but continued use of data collected up to that point. To safeguard data protection and confidentiality, the minimum personally-identifiable information possible will be collected.

## 6 STUDY ASSESSMENTS

### 6.1 STUDY ASSESSMENTS

The intervention provided will be dependent on the patients' needs however it will comprise of an electronic environmental control system which will help them to access devices around their home independently. An example system would consist of a controller (e.g. Qwayo 2) with a switch and mounting system and any additional peripherals (e.g. remote controlled sockets). The assessment for the system will take place first and can take between 30-60 minutes. Questionnaires will be completed afterwards and will take approximately 30 minutes to complete.

Assessment	Screening	Baseline (Assessment)	3 weeks following provision	8 weeks following provision
Assessment of Eligibility Criteria				
Written informed consent				
Demographic data (name, age, address) contact details				
Questionnaire				

### 6.2 LONG TERM FOLLOW UP ASSESSMENTS

The longest follow up will be 8 weeks.

## 7 DATA COLLECTION

All data will be collected by a Clinical Scientist within NHS Lothian's Environmental Control Service.

1. Participant will complete pre-intervention questionnaire **PROMIS Global10- score, PIADS-10 and study specific questions** (completed in person at assessment)
2. Intervention with environmental control equipment (prescription dependant on patient requirements)
3. Participant will complete post intervention questionnaire **PROMIS Global10- score, PIADS-10 and study specific questions** (3 weeks) (follow up over phone)
4. Participant will complete post intervention questionnaire **PROMIS Global10- score, PIADS-10 and study specific questions** (8 weeks) (follow up over phone)

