### **9.2 PROPOSED ANALYSES**

Incomplete datasets will be removed before undertaking the analysis.

The data will be analysed with descriptive methods with a focus on clinical significance. Correlation analysis will be conducted to determine relationships between the device use and social context and the mental health outcome measures.

For all of the outcome measures the following data will be reported: mean, change in mean between intervals and standard deviation.

Spearman Rank Correlation Coefficient will be used to test the significance of the relationship between variables.

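### Every baseline is taken in person and every follow-up by phone, so any effect of mode is inseparable from the baseline-to-follow-up change

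*Combined protocol and SAP*

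**What the plan says.** Section 7 (Data collection) sets the mode for each of the three questionnaire points. The baseline is "completed in person at assessment", before the equipment is supplied. The two later points are marked "3 weeks) (follow up over phone" and "8 weeks) (follow up over phone". Section 6.1 places the baseline in the same visit as the equipment assessment: "Questionnaires will be completed afterwards and will take approximately 30 minutes to complete".

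The design in section 3 is a "Case series (follow-up) design", with no comparison group. Section 2.2.1 states: "The co-primary endpoints are the PROMIS Global10 and PIADS-10 measures". For every outcome measure, section 9.2 will report "mean, change in mean between intervals and standard deviation". On the number of participants, section 4.1 says "it is expected to be <10".

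No section offers another mode at any point, asks for the mode to be recorded, or plans a comparison or adjustment for mode. Section 3 says that the study takes place in the home. That fits the assessment visit, but it does not turn the telephone follow-ups into visits.

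**The concern.** Both co-primary endpoints are self-reports about mental health, quality of life and the impact of a device. A person may answer such questions differently with a member of the service in the room than over the telephone. If so, the difference enters every baseline-to-3-week and baseline-to-8-week change. With no comparison group there is nothing to subtract it against.

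These changes are the main result. The background section promises measurement before and after the intervention, section 2.2.1 puts the focus on the clinical significance of the descriptive results, and section 1.2 wants the findings to inform a national service specification. Most weaknesses of an uncontrolled series come with the design. This one comes from a scheduling choice that can be changed beforehand and cannot be repaired once the data are in.

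**Working it through.** The plan states no power, effect size or standard deviation, so there is no figure of its own to reproduce. The question is whether a mode effect could be separated from the before/after change.

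**Inputs.** Modes by time point are from section 7, and the absence of a comparator is from section 3. The number of participants is taken as 9 for illustration, the largest value consistent with section 4.1.

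**Step 1: set the points side by side.**

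| Time point | Post-device | Phone |
|---|---|---|
| Baseline | 0 | 0 |
| 3 weeks | 1 | 1 |
| 8 weeks | 1 | 1 |

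The two indicator columns are identical for every participant, so their correlation is 1.0.

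**Step 2: write the expected changes.** Let *a* be a participant's level in person before the device, *D3* and *D8* everything else that has changed by 3 and 8 weeks (the device effect plus any effect of time, expectation or regression to the mean), and *M* the effect of answering by phone rather than in person.

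- Baseline: *a*
- 3 weeks: *a + D3 + M*
- 8 weeks: *a + D8 + M*
- Change to 3 weeks: *D3 + M*
- Change to 8 weeks: *D8 + M*
- Change from 3 to 8 weeks: *D8 − D3*, in which *M* cancels

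As an illustration, a mean change of 2 points fits *D* = 2 with *M* = 0, *D* = 0 with *M* = 2, and *D* = 4 with *M* = −2 equally well.

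**Step 3: rank of the planned design.** Take one column per participant, a post-device indicator and a phone indicator.

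- Single post-device effect: 9 + 1 + 1 = 11 columns, rank 10.
- Separate 3- and 8-week effects: 9 + 2 + 1 = 12 columns, rank 11.

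Each further participant adds one column and one to the rank, so the deficit of one stays at any sample size.

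**Step 4: what would remove the deficit.**

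- One mode for a participant at all three points: *M* is in all three values and cancels from every change.
- Some baselines by phone (4 of 9 in the check): full rank, 11 of 11 and 12 of 12, on the assumption that mode and post-device effects are common to all participants.
- Only the 8-week point moved to in person: full rank (11 of 11) only if the device effect is assumed equal at 3 and 8 weeks; otherwise still 11 of 12.

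The first option is the only one of the three that needs no model.

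**Step 5: what the switch does not touch.** The 3-to-8-week change lies within one mode, though it does not answer the before/after question. The Spearman correlations in section 9.2, where they relate variables measured at the same time point, also lie within one mode.

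**The case against.** The strongest reply is that the point is small beside the study's other limits. The study is exploratory, unpowered and descriptive. Time, expectation, regression to the mean and data collection by the providing service all coincide with before/after as well, and would remain with one mode throughout. Sampling error is also large. With 9 participants and a standard deviation of change of 1 SD (an assumption), the standard error of a mean change is 1/√9 = 0.33 SD, and the 95% half-width is 2.306 × 0.33 ≈ 0.77 SD. A modest mode effect would be hidden within that. All of this stands. It limits what alignment can achieve, but it does not make the mode switch separable.

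There is also a fair objection to moving the baseline to a call. The visit happens anyway, a call can be missed, and section 9.2 removes incomplete datasets. One loss among 9 is 1/9 = 11% of the sample. This stands too, and it is why a fallback is needed.

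A reader might infer three further things that the documents do not support:

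- **A bias of a given size.** An assumed mode effect of 0.1 to 0.3 SD against an assumed change of 0.5 SD would give 0.1/0.5 = 20% to 0.3/0.5 = 60%. Both values are assumptions with no source in the protocol, and the direction is unknown, so benefit could be masked as easily as inflated.
- **A switch from silent form-filling to answering aloud.** Section 7 says only in person and by phone. It uses the same wording for completion at all three points and has a Clinical Scientist collect all data. Some baselines may well be answered aloud.
- **Loss of participants with impaired speech.** No section mentions speech. Section 5.1 has patients contacted by telephone to arrange the assessment, which suggests that phone contact is usual, although it does not show that each can manage a long questionnaire call. Deletion of incomplete datasets is a separate matter.

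**Conclusion.** The point holds as one of identifiability. As planned, the changes from baseline in PROMIS Global10 and PIADS-10 contain any in-person-to-phone effect in full, and no analysis of these data alone can take it out, whatever the number recruited. This rests only on the modes in section 7 and the lack of a comparator in section 3.

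It is not a demonstrated bias: the documents give no size or direction for a mode effect. Nor would one mode make the change an estimate of the device effect, because it removes one of several before/after confounders. The switch should be changed because it is avoidable at small cost, but it does not undermine the study as a descriptive series.

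**What to change.** Amend section 7, and the form described in section 7.2, as follows.

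1. Each participant answers in one mode at all three points. The questions are read aloud from the same script each time, and the mode is recorded on the form.
2. By default this means a baseline phone call after written consent at the assessment visit (sections 5.2 and 11.2.1) and before provision. Section 3 implies a variable wait for equipment, which should leave room for the call. It can be booked at the visit.
3. A participant who cannot use the phone uses one alternative mode at all three points.
4. If the baseline call cannot be made before provision, the baseline is taken in person, still before the device is in use, with the same read-aloud script. The mode is recorded, the data are kept rather than treated as incomplete under section 9.2, and the mode difference is stated as a limitation.

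If the sponsor keeps the present schedule, the minimum is a common script, a recorded mode and a stated limitation.

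**Cost.** An amendment to the protocol and form wording. The questionnaire time of about 30 minutes moves from the visit to a call, with no extra staff. The downside is one extra call to arrange and a small risk that it is missed, for which the documents give no figure and which the in-person fallback covers.

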### 7.1 Source Data Documentation

1. PIADS10 Questionnaire.
2. PROMIS Global 10 Questionnaire.
3. Study Specific Questions Questionnaire.

## 7.2 Case Report Forms

Collect data on structured form – will be transcribed onto database (spreadsheet).  
Handwritten forms will be kept locked in cabinet.

# 8 DATA MANAGEMENT

[figure not shown]
## 8.1.1 Personal Data

The following personal data will be collected as part of the research:

- Name, ReTIS number (this is 6 digit identifier used by the ReTIS database – the system used for patient management within the SMART Centre for issuing wheelchairs and environmental control systems etc.), Phone number, Home address, health conditions. This information is collected from the patient's referral form.

Personal data will be stored by the research team on ReTIS (Local data management software) which is password protected. A mapping spreadsheet will be created to map between the ReTIS number and the participant's study specific code. Personal data will be stored for as long as they are a patient of the Environmental Control Service.

## 8.1.2 Data Information Flow

\* After a fixed period in accordance with the retention of health records requirements.

### **8.1.3 Transfer of Data**

Data collected or generated by the study (including personal data) will not be transferred to any external individuals or organisations outside of the Sponsoring organisation(s).

### **8.1.4 Data Controller**

A data controller is an organisation that determines the purposes for which, and the manner in which, any personal data are processed.

NHS Lothian are data controller along with any other entities involved in delivering the study that may be a data controller in accordance with applicable laws (e.g. the site)

### **8.1.5 Data Breaches**

Any data breaches will be reported to the NHS Lothian Data Protection Officer who will onward report to the relevant authority according to the appropriate timelines if required.

## **9 STATISTICS AND DATA ANALYSIS**

### **9.1 SAMPLE SIZE CALCULATION**

Due to the data will analysed with descriptive methods no sample size calculations are required.

### **9.2 PROPOSED ANALYSES**

Incomplete datasets will be removed before undertaking the analysis.

The data will be analysed with descriptive methods with a focus on clinical significance. Correlation analysis will be conducted to determine relationships between the device use and social context and the mental health outcome measures.

For all of the outcome measures the following data will be reported: mean, change in mean between intervals and standard deviation.

Spearman Rank Correlation Coefficient will be used to test the significance of the relationship between variables.

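### Section 9.2 removes incomplete datasets without defining them; read at participant level, one missed call deletes all of a person's observed data in a study of fewer than 10

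*Combined protocol and SAP*

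**What the plan says.** Section 9.2 opens with the rule "Incomplete datasets will be removed before undertaking the analysis". It then plans means, changes in mean between intervals and standard deviations for every outcome, plus Spearman correlations. Because removal comes before the analysis, it governs all of these. No definition of incomplete, available-data summary, reporting of missing data or sensitivity analysis is given anywhere.

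The setting is small and has repeated measures:

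- On the number of participants, section 4.1 says "it is expected to be <10".
- Section 3 states: "Participants will be involved from their assessment until 8 weeks after device provision".
- Section 7 has each participant complete "PROMIS Global10- score, PIADS-10 and study specific questions" three times: in person at assessment, then by phone at 3 and 8 weeks.
- Section 2.2.1 states: "The co-primary endpoints are the PROMIS Global10 and PIADS-10 measures". It adds that "due to predicted low participant numbers this study has not been powered to assess these endpoints".
- Section 5.2.1 lists one withdrawal option, from "all aspects of the trial but continued use of data collected up to that point", and asks for the main reason for withdrawal to be recorded if possible.

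**The concern.** In a case series the purpose is to describe what happened to the people enrolled. With at most nine of them, each observed change matters. On the participant-level reading, two kinds of person are lost unnecessarily:

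- someone with baseline and 3-week scores who misses the 8-week call loses a complete baseline-to-3-week change;
- someone who misses the 3-week call but answers at 8 weeks loses a complete baseline-to-8-week change, the longest follow-up in the study.

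A participant who withdraws before 8 weeks has an incomplete record on this reading, so section 9.2 would remove what section 5.2.1 allows to be used. Section 1.2 intends the results to inform a review of NHS Scotland provision. A reader there needs to know how many people had no usable result and why, and the plan makes no provision for showing it.

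**Working it through.** The plan gives no dropout rate, and section 9.1 says "no sample size calculations are required", so there is no stated figure to reproduce. What follows is an illustration.

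**Inputs from the protocol.** Fewer than 10 participants (4.1), so n = 9 is the largest case; two follow-up calls after a baseline visit, with three instruments each time (7).

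**Assumptions.** Baseline is complete for all nine. Each call is missed independently with probability m. The main values are 10% and 20%; 5% and 30% show the range.

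**Step 1: participant-level deletion.** A person is kept only if both calls are completed, so the expected number kept is 9(1 − m)².

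**Step 2: available pairs.** Baseline-to-3-weeks and baseline-to-8-weeks each need one call, so the expected number of pairs is 9(1 − m) for each.

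**Step 3: difference.** The gain per baseline interval is 9(1 − m) − 9(1 − m)² = 9m(1 − m). Over the two calls, 18m(1 − m) completed follow-up contacts are removed under deletion.

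| m | Kept under deletion | Pairs per baseline interval | Gain | Completed contacts removed |
|---|---|---|---|---|
| 5% | 8.12 | 8.55 | 0.43 | 0.86 |
| 10% | 7.29 | 8.10 | 0.81 | 1.62 |
| 20% | 5.76 | 7.20 | 1.44 | 2.88 |
| 30% | 4.41 | 6.30 | 1.89 | 3.78 |

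The chance that all nine are complete is (1 − m)¹⁸, which is 15% at m = 10% and 2% at m = 20%. The 3-to-8-week interval needs both calls, so nothing is gained there.

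**Step 4: permanent dropout.** If anyone who misses the 3-week call never returns, and m applies again at 8 weeks, 9(1 − m) people have 3-week data and 9(1 − m)² have 8-week data. Baseline-to-3-weeks still gains 0.81 or 1.44 people at 10% or 20%. Baseline-to-8-weeks gains none, since 7.29 or 5.76 remain either way. All nine baselines are kept instead of 7.29 or 5.76.

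**Step 5: how much the definition matters.** Three instruments on three occasions make nine forms. If one missing form removes the person, and forms go missing independently at 1%, 2% or 5% (assumed), 9(1 − q)⁹ gives 8.2, 7.5 or 5.7 people. If dataset instead means a single form on one occasion, only that form goes and the loss is small.

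**Step 6: direction of bias.** Suppose six completers change by +5 on average (hypothetical scores) and three people are removed.

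- Removed people at 0: mean for all nine is (6×5 + 3×0)/9 = 3.3, so the reported 5.0 is too high.
- Removed people at +5: mean for all nine is 5.0, so there is no bias.
- Removed people at +10: mean for all nine is (30 + 30)/9 = 6.7, so the reported 5.0 is too low.

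The documents contain nothing that selects among these.

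**The case against.** A reader might infer that the rule keeps mainly those who stayed well and kept the device, so that the results lean towards benefit. The documents do not support that as a finding. They give no dropout rate or expected reasons for missing data and do not mention device return; section 4.3 excludes rapidly deteriorating conditions; follow-up ends at 8 weeks and is by phone. It is a risk to guard against. Nor would available-pair summaries cure it for people with no follow-up at all: they have no change score and can only be listed.

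A reader might also infer that 9.2 flatly contradicts 5.2.1. It does so only if a withdrawn participant counts as an incomplete dataset. Section 5.2.1 permits continued use of the data; it does not promise that each withdrawn person enters every summary. This is a tension to be resolved.

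Other points in the plan's favour stand in part. The term is undefined, so the participant-level reading is the natural one but not the only one. A Clinical Scientist collects all data and may notice skipped answers. Removal affects the analysis, not the records: forms are kept (7.2) and study documentation is retained for at least 3 years (11.6), so a reanalysis would be possible. Nothing says that counts will be withheld. The study is unpowered and descriptive, so a loss of precision does not undermine a planned test of the co-primary endpoints.

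None of this rescues the sentence. It is a positive instruction to remove data, no other section limits it, and a descriptive aim is a reason to show everyone enrolled.

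**Conclusion.** The concern holds in a limited form. Section 9.2 contains an undefined deletion rule which, read at participant level, removes observed baseline and follow-up data from a study of at most nine expected participants and conflicts with the use of withdrawn participants' data. At 10% to 20% missed calls the cost is about 0.8 to 1.4 people per baseline-to-follow-up interval. With permanent dropout, the loss is confined to baseline and 3-week data. These figures rest on n = 9, complete baselines, independent missed calls and assumed rates; none of the rates comes from the documents.

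The case for change rests on the avoidable loss, the undefined term and the lack of any plan to show non-completers. It does not need a claim about which way the results would be biased. The plan should be corrected before analysis, but in an unpowered descriptive series this is not a flaw that invalidates the study.

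**What to change.** Replace the sentence in section 9.2 with wording such as:

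> All participants with a baseline questionnaire are included. Each timepoint and interval is summarised on everyone with the required values, with n shown. Participants without follow-up are listed with their available scores and the reason where known. A complete-case summary is a sensitivity presentation only.

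Two additions are needed. State how a questionnaire with missing items is scored; the documents give no rule, so one has to be specified. Reconcile 9.2 with 5.2.1 by saying that data collected before withdrawal enter the summaries for which they suffice.

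The cost is one paragraph and slightly longer tables, with no extra data collection: section 5.2.1 already asks for withdrawal reasons where possible. The downside is that n will differ between intervals. Each change must therefore be calculated within the people who have both values, not by subtracting two means taken over different people.

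### Section 9.2 tests Spearman correlations for significance in an expected fewer than 10 people, although the plan omits a sample size calculation because its analysis is descriptive

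*Combined protocol and SAP*

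**What the plan says.** Section 2.2.1 (Primary Endpoint) names PROMIS Global10 and PIADS-10 as co-primary and states that "due to predicted low participant numbers this study has not been powered to assess these endpoints". It continues: "Instead the data will be analysed with descriptive methods with a focus on clinical significance".

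Section 9.1 (Sample Size Calculation) relies on the same premise: "Due to the data will analysed with descriptive methods no sample size calculations are required".

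Section 4.1 lets recruitment fix the number: "The number of participants will be determined by how many participants it is possible to recruit within 12 months", and adds that "it is expected to be <10".

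Section 9.2 (Proposed Analyses) first drops incomplete datasets and repeats the descriptive intention. It then adds: "Correlation analysis will be conducted to determine relationships between the device use and social context and the mental health outcome measures". Its closing sentence makes this a test: "Spearman Rank Correlation Coefficient will be used to test the significance of the relationship between variables".

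The plan states no alpha, no sidedness, no list of pairs or time points, no multiplicity rule, no confidence intervals and no exploratory label for these correlations. No other significance test is planned.

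**The concern.** A significance test is inferential. The reason given in 9.1 for having no sample size calculation therefore does not cover the one inferential step in 9.2. At the expected size, a threshold of p<0.05 acts as a filter that only very large sample coefficients pass. A coefficient that passes will tend to be too big, and a moderate real relationship will usually fail.

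These would be the only planned p-values in the report. Section 1.2 says the evidence may be used in a review of Scottish provision and in writing a national service specification. A reader there could take a significant coefficient between device use and a mental health score at face value, or take a non-significant one as evidence of no relationship. The numbers support neither.

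**Working it through.** The plan has no power or sample size figure to reproduce. Its only numerical input is the expected number of participants.

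**Inputs from the protocol**
- n: fewer than 10 expected, so 9 is the most favourable case within that expectation (4.1). Complete-case analysis can lower it (9.2).
- Outcomes: two instruments (2.2.1), with follow-up at 3 and 8 weeks (section 7).
- Correlates: device use and social context (9.2).

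**Assumptions, because the protocol is silent**
- Two-sided 5% per test, unadjusted, with exact p-values and no ties.
- Bivariate normal data for the power figures.
- True correlations from 0.3 to 0.8.
- 4 to 8 tests.

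**1. Smallest coefficient that can be significant.** With D the sum of squared rank differences, r_s = 1 − 6D/[n(n²−1)]. Enumerating all n! orderings gives:

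| n | smallest significant absolute r_s | exact two-sided p there |
|---|---|---|
| 9 | 0.700 | 0.043 |
| 8 | 0.738 | 0.046 |
| 7 | 0.786 | 0.048 |
| 6 | 0.886 | 0.033 |
| 5 | 1.000 | 2/120 = 0.017 |
| 4 | none | lowest possible p = 2/24 = 0.083 |

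For example, at n=9 the boundary is D=36: 1 − 6×36/(9×80) = 1 − 216/720 = 0.70.

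**2. Power and overstatement** (simulation, 300,000 draws per cell; the true value is the underlying Pearson correlation):

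| true correlation | population r_s | power, n=9 | mean absolute r_s if significant, n=9 | power, n=6 | mean absolute r_s if significant, n=6 |
|---|---|---|---|---|---|
| 0.3 | 0.29 | 9% | 0.78 | 5% | 0.92 |
| 0.5 | 0.48 | 21% | 0.79 | 10% | 0.92 |
| 0.7 | 0.68 | 47% | 0.81 | 21% | 0.93 |
| 0.8 | 0.79 | 66% | 0.83 | 31% | 0.93 |

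If 0.5 is taken as the population Spearman value instead, power at n=9 is 23%. A true correlation near 0.5 would thus be reported as not significant in about 77-79% of studies (100 − 23 and 100 − 21).

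For a population r_s below 0.70, overstatement follows directly from step 1. With n of 9 or fewer, every significant coefficient is at least 0.70 in absolute value.

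**3. Chance of at least one false positive.** For k independent tests at level a it is 1 − (1−a)^k. With the exact n=9 level of 0.0433:
- k=4 (2 correlates × 2 instruments, one time point or change score): 1 − 0.9567⁴ = 16%.
- k=8 (both follow-ups): 1 − 0.9567⁸ = 30%.

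Letting the outcomes correlate up to 0.7 lowers these to about 15% and 24%. The range is therefore about 15-30%.

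**4. What an interval would show.** At n=9 with observed r_s = 0.5, Fisher's z with variance 1.06/(n−3) gives atanh(0.5) = 0.549 and SE = √(1.06/6) = 0.420. The limits are tanh(0.549 ± 1.96×0.420), which is −0.27 to 0.88. The alternative variance (1 + r_s²/2)/(n−3) gives −0.29 to 0.88.

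**5. What a powered test would need.** For 80% power, n = 1.06 × [(1.960 + 0.842)/atanh(ρ)]² + 3. At ρ=0.5 this is 1.06 × (2.802/0.549)² + 3, which rounds up to 31. The same formula gives 90 at ρ=0.3, 15 at 0.7 and 10 at 0.8.

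**The case against.** The strongest reply is about proportion. The objective is to explore (2.1.1), the design is a case series (section 3), and the lack of power is openly declared. The co-primary results are means, changes and standard deviations, which this analysis does not touch. A formal calculation would not change n, because 12-month recruitment fixes it. All of this stands, and it limits the severity. It does not remove the conflict, because 2.2.1 and 9.1 appeal to a descriptive analysis that 9.2 then departs from.

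Some stronger readings are tempting, but the documents do not support them:
- **Significant results would be mostly false.** This depends on an assumed share of real relationships. At n=9 and a true correlation of 0.5, the false share of significant results is 65%, 38% or 17% if 10%, 25% or 50% of tested pairs are real.
- **A non-significant result carries no information.** Power at n=9 is 66% for a true correlation of 0.8, so very strong relationships would be found more often than not.
- **At least eight tests will be run.** Section 9.2 does not say that both follow-ups are tested or that each instrument is tested separately. Four is equally compatible.
- **The p-values will be miscalibrated by a large-sample approximation.** The plan names no computation method, and exact p-values are possible.
- **The correlations would become the main evidence for a national specification.** Section 1.2 says only that the study contributes to an evidence base.

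Keeping exact p-values under a clear exploratory label, with 9.1 amended to match, would also reconcile the sections. It would leave the overstatement and low power in place.

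**Conclusion.** The point holds as an inconsistency between 2.2.1 and 9.1 on one side and the last sentence of 9.2 on the other, and nothing else in the protocol resolves it. At the expected size the tests are poorly informative for moderate correlations: the significance threshold is high, power is low, and the coefficients that pass it are inflated.

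These sizes depend on the assumed two-sided 5% level, on n staying at or below 9, and on the assumed number of tests. Ties in short ordinal scales would shift the exact thresholds somewhat. The conclusion is confined to the correlation findings, so it is a should-fix, not a must-fix.

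**What to change.** Replace the last sentence of 9.2 with wording such as:

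> Spearman coefficients will be reported descriptively with 95% confidence intervals and a scatter plot for each pair; no significance tests will be done, all pairs examined will be reported, and the results are hypothesis-generating.

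It would help to list the pairs and time points in advance. Sections 2.2.1, 9.1 and 9.2 would then agree, and 9.1 could stand unchanged in substance.

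The cost is a sentence or two of protocol text and no extra data. The small downside is that no p-value can be reported for these relationships.
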